Preliminary human data indicate curcumin supplementation improves surrogate markers of liver disease and of metabolic risk in NAFLD patients^{20, 21}. The combination of curcumin with phospholipids greatly improves oral bioavailability of curcumin, allowing greater systemic concentrations and delivery to target organs^{22, 23}, and curcumin-phosphatidylcholine phytosome complex administration for up to 18 months was well-tolerated, safe²⁴ and improved clinical end-points and inflammatory parameters in patients with osteoarthritis, uveitis and chronic kidney disease (CKD)^{25, 26, 27}.

2. Research Hypothesis and Aims

On the basis of above-mentioned data, we hypothesized that treatment with phytosomal curcumin would result in significant improvement in liver histology in patients with NASH.

Key secondary hypotheses include tolerability and safety of phytosomal curcumin and the potential to improve NASH-related CKD, systemic inflammation, glucose and lipid metabolism.

To test this hypothesis, we designed a phase II, multicentre, double-blinded, placebo-controlled randomized controlled trial (RCT).

3. Study Design setting and timeline

This is a 72-week, investigator-initiated, multicentre, randomized, double-blinded, placebo-controlled trial of treatment with phytosomal curcumin 1 g daily for adults with biopsy-proven NASH. Screening was undertaken within 14 days of randomisation to assess eligibility and collect baseline data. Patients who satisfied the eligibility criteria were randomly assigned (1:1) to receive oral phytosomal curcumin 1 g daily (experimental) or placebo (control). After which, a 12-week washout period is scheduled.

The trial will be conducted at two University hospitals (HUMANITAS Gradenigo, Turin, Italy, and Città della Salute e della Scienza, Turin, Italy) between May 25th, 2018 and Dec 30th, 2022.

The primary outcome measure will be assessed using an intention-to-treat analysis of the proportion of evaluable patients achieving an improvement in liver histology between liver biopsies at baseline (within 6 months of screening) and after 72 weeks of treatment. Histological improvement will be defined as a

combination of resolution of active steatohepatitis and no worsening in fibrosis (assessed by Kleiner Fibrosis score²⁸; detailed in outcome section).

4. Ethics and regulatory approval

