5.4 Intervention

5.4.1 Experimental arm (phytosomal curcumin)

Phytosomal curcumin Meriva® (Indena S.p.A. Milan, Italy) 1,000 mg (active experimental group)(Indena s.p.a., Milan, Italy) was supplied was administered before meals at a dose of 1000 mg twice daily 12 hours apart (total daily dose: phytosomal curcumin Meriva 2000 mg, corresponding to 400 mg curcuminoids).

Participants were encouraged to take phytosomal curcumin at the same time each day, according to the most convenient time for them. All tablets were produced and sponsored by the manufacturer who otherwise had no role in the study design, data collection, data analysis, data interpretation or publication of this manuscript. Placebo and Meriva® tablets contained the same ingredients except for curcuminoids. For simplicity, Phytosomal curcumin tablets will be referred to as curcumin in the following. Compliance will be considered acceptable if more than 75% of dosages will be ingested. Participants reported missed dosages, concomitant medication, and adverse events during the trial.

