Both active treatment (phytosomal curcumin) and placebo control will be packaged and labelled with a unique identification number (in keeping with the European Unions Good Manufacturing Practice for Medicinal Product guidelines) by the manufacturer (Indena S.p.A.), to the extent that the receiving trial site will be blinded to the study drug throughout the duration of the trial. Sealed parcels (containing electronic information) will be sent with each drug package for the attention of the unblinded members of the central trial management group (TMG) nominated statistician, RG and database programmer, EP, to ensure (1) safe delivery of the correct drug and (2) blinding of the treatment allocation from the remainder of the TMG and the trial patient. Unblinding of treatment will only take place if the identity of the allocated study medication will be necessary for patient safety and care. If a serious adverse event (SAE) is deemed unexpected and possibly, probably or definitely related to phytosomal curcumin (ie, suspected unexpected serious adverse reaction=SUSAR), a clinical member of the TMG was unblinded to the medication to evaluate causality and subsequently label the event either as an unrelated SAE (for patients receiving placebo) or a SUSAR (for patients receiving phytosomal curcumin). The latter will be reported to the MHRA and the NRES, and only if patient safety is jeopardised the study medication will be discontinued and the treating clinician/patient informed.

6. Trial schedule and data collection

The trial will involve nine patient-related visits at their nearest trial site (**Figure 1**).

The study comprises four stages: (1) screening, enrollment, randomisation and baseline investigations (visits 1 and 2, over a maximum period of 14 days), (2) 504 days of study treatment (visits 3–7, over 72 weeks), (3) primary endpoint assessment including liver biopsy (visit 8, within 1 day of the EOT) and (4) post-treatment follow-up assessment (visit 9, 12 weeks after EOT). If the trial investigating team or the trial participant suspected an AE, an unscheduled visit was arranged within 24 h. Each visit included patient interview, clinical examination, anthropometry and blood/urine chemistry.

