-Improvement in anthropometry, physical activity and dietary parameters (body weight, BMI, waist circumference), physical activity and daily dietary consumption.

-Improvement in glycaemic control (fasting plasma glucose, HbA1c)

-Improvement in cardiovascular risk profile: fasting plasma lipids, oxidative stress markers, inflammatory markers/adipokines and chemokine MCP-1.

-Chronic kidney disease (CKD) regression. CKD will be defined according to Kidney Disease Improving Global Outcomes (KDIGO) guidelines as sustained (i.e., documented on 2 occasions at least 3 months apart) reduction in estimated Glomerular Filtration Rate [eGFR] <60 mL/min/1.73 m² **and/or** sustained increase in albumin excretion rate (AER) ≥30 mg/d. CKD regression will be defined as sustained (i.e., documented 3 month apart, on both follow-up visit 7 and visit 8) estimated Glomerular Filtration Rate [eGFR] ≥60 mL/min/1.73 m² **and** normalization of AER (i.e., <30 mg/d).

eGFR will be assessed from serum creatinine using the **CKD-EPI** (Chronic Kidney Disease Epidemiology Collaboration) equation, as recommended by KDIGO guidelines⁴². eGFR and AER will be classified according to KDIGO categories⁴³

-Change in absolute values of eGFR^{44, Error! Bookmark not defined.}, and of albumin excretion rate(AER).

We will estimate mean annual rates of change in eGFR from baseline to the final follow-up visit (total slopes), within each treatment allocation using linear mixed model repeated measures (MMRM);

adjustments were made for age, baseline eGFR, baseline urinary AER, diabetes, baseline fibrosis stage, systolic blood pressure, angiotensin-converting enzyme/angiotensin receptor blocker⁴⁵(see. **supplementary material**)

Exploratory outcomes

We explored the effect of treatment on Nuclear Factor(NF)-kB activation in the liver and in circulating mononuclear cell(MNCs). NF-kB is a key proinflammatory transcription factor involved in NASH development and progression and a known molecular target of curcumin (see Methods and supplementary material).

Safety outcomes

Safety end points include adverse events after the start of treatment, biochemical assessments, and clinical assessments. Selected events (including deaths, cardiovascular events, and acute pancreatitis) were adjudicated by an independent, external event-adjudication committee, whose members were unaware of the treatment assignments. A complete list of the trial end points is provided in protocol Table 1.

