We estimated mean annual rates of change in eGFR from baseline to the final follow-up visit (total slopes), by treatment allocation using linear mixed model repeated measures (MMRM); adjustments were made for age, sex, first baseline CKD stage, baseline eGFR; baseline urinary ACR, diabetes, history of cardiovascular disease, systolic blood pressure, angiotensin-converting enzyme/angiotensin receptor blocker use⁷⁹

Proteinuria will be estimated using measurements of urinary protein and creatinine at baseline and at baseline and at each visit thereafter.

Albuminuria and eGFR stage will be categorized according to the KDIGO classification system⁸⁰

The end-stage renal disease was defined as kidney transplantation or the receipt of dialysis for at least 30 days unless death occurred.

For exploratory outcomes, we will explore the existence of a threshold in hepatic NF-kB activation change predicting histological response (NASH resolution, fibrosis improvement) using the area under receiver operating characteristic curve (AUROC) analysis and Youden index.

A sensitivity analysis will be performed in which missing data were handled by reference-based multiple imputation informed by data from placebo recipients (see **Preplanned subgroup and sensitivity analyses suhealing**).

Safety will be analysed descriptively

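### After unblinding, the causality label of an unexpected, possibly related SAE is set by treatment arm, so any between-arm summary of related unexpected SAEs built on that label is one-sided

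*Protocol*

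**What the plan says.** The rule is in Protocol section 5.5, under medication preparation and blinding/unblinding. It is triggered by an SAE "deemed unexpected and possibly, probably or definitely related to phytosomal curcumin". Then "a clinical member of the TMG was unblinded to the medication to evaluate causality", and this person is to "label the event either as an unrelated SAE (for patients receiving placebo) or a SUSAR (for patients receiving phytosomal curcumin"). The SUSAR label has a stated use: "The latter will be reported to the MHRA and the NRES".

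Other parts of the Protocol bear on what the label can affect:

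- Section 2: "Key secondary hypotheses include tolerability and safety of phytosomal curcumin".
- Section 7, safety outcomes: "Safety end points include adverse events after the start of treatment, biochemical assessments, and clinical assessments". Nothing there restricts the endpoint by causality.
- Section 7, AE reporting and analysis: investigators evaluate and record every SAE and adverse reaction. A committee unaware of assignment at ascertainment adjudicates the nature and number of SAEs. The central trial office assesses each AE for seriousness, causality and expectedness.
- Section 9.2: "Safety will be analysed descriptively".
- Section 5.4.1: "Placebo and Meriva® tablets contained the same ingredients except for curcuminoids".

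**The concern.** Blinded attribution is useful in a placebo-controlled trial because both arms are judged by the same rule. Some events will be called possibly related in either arm. As long as nobody knows the allocation, that background level can be expected to be the same on both sides, and it cancels in the comparison. Section 5.5 breaks this symmetry for one class of event. A judgement of possible, probable or definite relatedness stands if the patient took curcumin and becomes unrelated if the patient took placebo.

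Unblinding to decide whether an event needs SUSAR reporting is reasonable. Here, however, the step is described as an evaluation of causality, and its output is a causality label fixed by arm. If that label reaches a table of related SAEs, ordinary background attribution appears as an excess on curcumin. With a descriptive safety analysis, such a row would be read at face value.

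**Working it through.** **1. What the rule does to each event.** The protocol states no figure on this point, so there is none to reproduce. Take an SAE judged, before unblinding, unexpected and at least possibly related:

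| Arm | Judgement before unblinding | Label after unblinding | Counted as an SAE? | Counted as related under the final label? |
|---|---|---|---|---|
| Curcumin | at least possibly related | SUSAR | yes | yes |
| Placebo | at least possibly related | unrelated SAE | yes | no |

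The last column depends on the arm alone. The fourth column does not depend on it, so the total SAE count per arm is unchanged.

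**2. Whether another provision protects the causality value.** The blinded adjudication in section 7 covers the nature and number of SAEs, not relatedness. The trial office's assessment in the same section does include causality, so causality is collected, but the section does not say whether the value before or after unblinding is kept. The only relabelling instruction in the protocol is the arm-dependent one in section 5.5.

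**3. Size, by assumption.** Inputs: 52 patients to be recruited (section 5.1) and 1:1 allocation (section 5.5), so n = 52/2 = 26 per arm. The rate p of patients with an SAE judged, while blinded, unexpected and related is not given. I assume it is equal in both arms, with patients independent, and take 2% to 20% as the range.

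- Expected count per arm = 26p.
- Probability that curcumin shows at least one such event = 1 − (1 − p)^26.

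| Assumed p, both arms | Expected, blinded judgement kept (curcumin v placebo) | Expected, final label (curcumin v placebo) | P(curcumin shows at least one) |
|---|---|---|---|
| 2% | 0.5 v 0.5 | 0.5 v 0 | 1 − 0.98^26 = 41% |
| 5% | 1.3 v 1.3 | 1.3 v 0 | 1 − 0.95^26 = 74% |
| 10% | 2.6 v 2.6 | 2.6 v 0 | 1 − 0.90^26 = 94% |
| 20% | 5.2 v 5.2 | 5.2 v 0 | 1 − 0.80^26 = over 99% |

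As an example, 3 v 3 by blinded judgement would be displayed as 3/26 (11.5%) v 0/26.

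**4. Would a test be misled?** No test is planned, so this only gives scale. For k v 0 with 26 per arm, the two-sided Fisher p-value is 2·C(26,k)/C(52,k): 0.235 for k = 3, 0.051 for k = 5 and 0.023 for k = 6. With equal true rates, the chance of p ≤ 0.05 using final labels, against using blinded labels, is 0.0% v 0.0% at a rate of 2%, 0.15% v 0.10% at 5%, 4.0% v 1.0% at 10% and 42% v 2.3% at 20%. At 10% or below, the harm is therefore a misleading display and not a frequent false significance.

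**The case against.** The strongest reply is that the label serves reporting only. Section 5.5 follows it directly with onward reporting, one person is unblinded, and section 7 separately has the investigators evaluate and record SAEs. Nothing says that the investigator's own causality entry is changed. Which value goes into the tables could also be settled in a statistical analysis plan, which is not at hand. This stands as far as it goes: overwriting of the record cannot be shown, and the absence of a table specification is not a fault. It does not remove the point, because the protocol itself fixes an arm-dependent rule and calls it an evaluation of causality.

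A second reply is that the question asked is relatedness to phytosomal curcumin, and a placebo patient received none, so unrelated is simply the logical answer. In that narrow sense it is correct. But a label that can only be positive in one arm carries no comparative information. A bare unrelated also says more than not related to curcumin: on the section 5.4.1 description, a reaction to a shared tablet ingredient could occur in either arm.

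Three stronger readings are tempting and are not supported:

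- A reader might infer that the whole safety comparison is biased. The safety endpoint has no causality restriction, all SAEs are recorded, and a relabelled placebo event remains an SAE in its arm.
- A reader might infer that the committee's six-monthly reviews carry the distortion. Section 7 describes no tables by causality and says that the committee is unblinded when it advises.
- A reader might point to 6 v 6 shown as 6 v 0, with p about 0.02. That needs 6/26 = 23% per arm, above the whole range assumed here, and a test that nobody plans.

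**Conclusion.** The point holds in a limited form. Under section 5.5 the final causality label of an unexpected SAE already judged at least possibly related is determined by arm, so a between-arm summary of such events built on that label has a placebo count of 0 by construction. The direction is certain: against curcumin. The size rests on an assumed equal rate and 26 per arm. At rates of 2% to 10%, curcumin would show at least one event with probability 41% to 94%, with 0.5 to 2.6 events expected. The effect is confined to summaries that use the final causality label; all-AE and all-SAE counts and the efficacy endpoints are untouched. Whether any planned summary uses that label is not stated. Severity: minor.

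**What to change.** Amend the unblinding paragraph of Protocol section 5.5 to state that:

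1. the causality judgement made before unblinding is kept unchanged and is the value used, for both arms, in every safety summary that involves causality;
2. the unblinded allocation serves only to decide whether the event is reported as a SUSAR;
3. all SAEs are shown by arm regardless of causality.

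The instruction to label placebo events unrelated then goes. Such an event could be recorded as related by blinded assessment, allocation placebo, not reported as a SUSAR.

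The cost is one paragraph of amendment and, if the case report form has no place for it, one field for the judgement before unblinding. The downside is that some placebo SAEs will appear as related by blinded assessment and need a footnote. With equal rates, the expected counts of related unexpected SAEs then match between arms, for example 1.3 v 1.3 at 5% in place of 1.3 v 0.

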5.2 Inclusion criteria

The trial entry criteria will be based on a diagnosis of 'definite' NASH on liver biopsy obtained within 6 months of screening. Throughout the study, all liver biopsies will be read centrally by one single (RP) expertised pathologist from the central trial site (HUMANITAS Gradenigo), blinded to clinical and laboratory data and to treatment allocation: prior to randomisation, the liver histopathologist will review all of the liver biopsies of the potential participants to assess whether a diagnosis of 'definite' NASH is present.

A 'definite' diagnosis of NASH is defined if all of the following are present on biopsy: (1) macrovesicular steatosis (>5%); (2) hepatocyte ballooning (\pm Mallory Hyaline) and (3) lobular inflammation (mixed infiltrate, related to foci of ballooning). Only patients with 'definite' NASH will be classified as eligible. All participants are to be ≥ 18 to <70 years of age and have a BMI ≥ 25 kg/m² at screening. Patients with type 2 diabetes mellitus (T2DM) at screening had to have stable glycaemic control (HbA1c <9%) and be managed by either diet and/or a stable dose of metformin/sulfonylurea/s. Patients without a history of T2D prior to the screening visit will undergo a 75-g standard OGTT and/or have their HbA1c measured at screening to determine their glycaemic status and will be labelled as 'non-diabetic' if one or more of the following was confirmed

- Impaired fasting glucose, defined using the European Criteria between 110 and 126 mg/dL.
- IGT, defined as 2 h plasma glucose levels between 140 and 200 mg/dL on the 75 g OGTT.
- Normal Fasting Plasma Glucose <110 mg/dL and normal 2 h plasma glucose levels <140 on the 75 g OGTT.
- HbA1c <6.5%

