5.3 Exclusion criteria

A detailed summary of the exclusion criteria is provided in **box 1**. In brief, patients with a history or current significant alcohol consumption, poor glycaemic control (HbA1c >9.0%), Child's Pugh B or C cirrhosis or other liver disease aetiology were excluded. The latter was confirmed with a full liver aetiology screen (drug induced, viral hepatitis B/C, autoimmune and genetic) at the screening visit. Past and current alcohol consumption was ascertained by a detailed review of the patient's medical, social history and by a validated, self-administered food frequency questionnaire with reference pictures to remind participants of drink equivalents (see dietary record section). Concomitant use of drugs reported to be inducers (methotrexate, amiodarone, steroids) or potential therapies for NASH (TZDs, GLP-1 analogues, vitamin E), or other known hepatotoxins were assessed during the screening visit (**box 1**).

Box 1. Exclusion criteria

1. Refusal or lacks capacity to give informed consent to participate in the trial.
2. Participation in any clinical trial of an investigational therapy or agent within 12 months of randomisation.
3. Patient (or carer) deemed not competent at using the correct site and technique for subcutaneous injection of the trial treatment (containing dummy drug on practice).
4. NAFLD Activity Score (NAS) <3 on liver biopsy.
5. Child's B or C cirrhosis or clinical evidence of decompensated chronic liver disease: radiological or clinical evidence of ascites, current or previous hepatic encephalopathy and evidence of portal hypertensive haemorrhage or varices on endoscopy.
6. Medical history of multiple drug allergies (defined as anaphylactoid drug reactions in >2 drug groups) or allergy to curry or curcumin-based nutraceuticals
7. Presence of any acute/chronic infections or illness that at the discretion of the chief investigator might compromise the patient's health and safety in the trial.
8. Pregnancy or breastfeeding.
9. Women, of childbearing age, who are not willing to practise effective contraception (ie, barrier, oral contraceptives, impenon or past medical history of hysterectomy) for the 48-week duration of the trial and for 1 month after the last administration of the drug.
10. Liver disease of other aetiologies (ie, drug-induced, viral hepatitis, autoimmune hepatitis, PBC, PSC, haemochromatosis, A1AT deficiency, Wilsons disease).

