5.5 Randomization, stratification and blinding

Randomization and stratification

Participants meeting all the eligibility criteria and providing written informed consent will be randomized centrally on a 1:1 basis to either of the two-study treatments (phytosomal curcumin vs placebo) using computer generated randomization. To ensure even distribution between groups in key baseline covariates, randomization will be stratified into blocks of 4 according to the following variables: diabetes status (present vs. absent), obesity status (present vs. absent), fibrosis stage (stage F3-4 vs. stage 0-2), CKD (present vs. absent). Trial participants will be allocated a unique trial identification number to preserve patient confidentiality and enable the study to be double-blinded. Patients, investigators, assessors, trial site staff, and the sponsor (except for specific laboratory staff and individuals responsible for safety) remained blinded to treatment assignment throughout the trial.

Medication preparation and blinding/unblinding procedures

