Histological NASH resolution (defined by the NASH Clinical Research Network as no more than mild residual inflammatory cells [score of 0 or 1] and no hepatocyte ballooning [score of 0]) **and** no worsening of liver fibrosis (with worsening defined as an increase of one stage or more on the Kleiner fibrosis classification scale) after 72 weeks, in line with regulatory perspectives^{31,32}.

Secondary outcome measures

Liver-centered histological outcomes:

1) a ≥ 1 stage improvement in fibrosis and no worsening of NASH (with worsening defined as an increase of ≥ 1 point in either the lobular inflammation score or the hepatocyte ballooning score according to the NASH Clinical Research Network criteria) after 72 weeks

2) improvement in clinically significant fibrosis³³, defined by the proportion of patients with baseline fibrosis stage ≥ 2 who have fibrosis stage 0-1 at EOT, without worsening of NASH.

3) improvement in advanced fibrosis, defined by the proportion of patients with baseline fibrosis stage 3-4 who have fibrosis stage 0-2 at EOT, without worsening of NASH.

3) a ≥ 2 -point improvement in NAFLD activity score (NAS), with at least 1 point improvement in either ballooning or lobular inflammation score;

4) individual components of the NAFLD activity score (steatosis, hepatocyte ballooning, lobular inflammation) and the Kleiner fibrosis stage. Fibrosis stages 1a, 1b, and 1c were considered stage 1 for the purposes of analysis.

Liver-centered non-histological outcomes:

4) changes from baseline to 72 weeks in serum liver enzyme concentrations, improvement in noninvasive markers of liver disease severity, including computerized sonographic hepato-renal ratio (which correlates closely with histologic and ¹H magnetic resonance spectroscopy steatosis^{34,35, 36,37,38}, see **Analytical**

Methods subheading), serum cytokeratin-18 fragments(a marker of NASH), NAFLD fibrosis score, FIB-4 and serum lumican (as markers of fibrosis)(see supplementary material).

The extracellular matrix proteoglycan lumican was chosen because its circulating levels have been shown to be a reliable marker not only of hepatic fibrosis but also of active hepatic fibrosis deposition, its expression is upregulated by Nf-kB, and its levels have been shown to differentiate histologically progressive, fibrosing NASH from mild, nonprogressive NAFLD^{39, 40, 41}

Non liver-centered outcomes

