9.3 Methods in analysis to handle missing data

The primary imputation method for missing data will be the non-responder imputation for primary and secondary dichotomous outcomes. This approach does not rely on an assumption of missing at random and is considered conservative for estimating the treatment effect.

To investigate the sensitivity of the histological results with regard to the handling of missing

data, post-hoc sensitivity analyses using multiple imputation will be conducted. These analyses are based on the same CMH method as for the main analyses but using a multiple imputation at random method for missing data(see following Subheading)

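### Secondary outcome 1 (fibrosis improvement) has no baseline-stage restriction, so stage 0 patients, who cannot improve, count as non-responders and shrink the difference in proportions

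*Protocol*

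**What the plan says.** - **Outcome.** Protocol Section 7, liver-centered histological outcomes, item 1: "a ≥ 1 stage improvement in fibrosis and no worsening of NASH" after 72 weeks. No baseline stage is required.
- **Neighbouring items.** The next two outcomes do limit their denominators. One is "defined by the proportion of patients with baseline fibrosis stage ≥ 2 who have fibrosis stage 0-1 at EOT"; the other is "improvement in advanced fibrosis, defined by the proportion of patients with baseline fibrosis stage 3-4 who have fibrosis stage 0-2 at EOT". Both add the condition that NASH has not worsened.
- **Entry.** Section 5.2: "Only patients with 'definite' NASH will be classified as eligible". That diagnosis rests on steatosis, ballooning and lobular inflammation. Section 5.3 (Box 1) excludes "NAFLD Activity Score (NAS) <3 on liver biopsy". Fibrosis is part of neither the diagnosis nor the score.
- **Scale.** Section 8.1.1 stages fibrosis from F0 to F4, so F0 is the floor.
- **Strata.** Section 5.5 stratifies by "fibrosis stage (stage F3-4 vs. stage 0-2". Section 9.2 adjusts for the stratification variables, and the prespecified subgroups use the same split.
- **Analysis.** Section 9.2 compares categorical outcomes between arms as proportions, by chi-square or Fisher test, and calls this analysis unpowered. It also plans adjusted relative risks.
- **Missing data.** Section 9.3 applies "non-responder imputation for primary and secondary dichotomous outcomes".

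**The concern.** A patient who enters at stage 0 cannot have a one-stage fall, whatever the treatment does. If such patients stay in the denominator of outcome 1, they are fixed failures in both arms. The reported response rates and their difference then understate what happens in patients who have fibrosis to lose, and the test has somewhat less power. The fibrosis stratum pools stage 0 with stages 1 and 2, so neither the randomisation nor the planned adjustment separates patients who can respond from those who cannot. The same list already uses at-risk denominators for two related outcomes, which makes item 1 inconsistent with its neighbours.

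**Working it through.** **The Protocol's own figure.** Section 9.1 gives no figure for the fibrosis outcome. Its single-stage rule (at least 8 responders of 21) concerns the primary outcome. It is reproduced with a null rate of 0.20 and a target of 0.50, rates inferred here: P(X ≥ 8 | 21, 0.20) = 0.043 and P(X ≥ 8 | 21, 0.50) = 0.905. Nothing in it depends on outcome 1.

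**Inputs.**
- 52 patients, 1:1, so 26 per arm (Sections 5.1 and 5.5).
- Stage 0 share *f*: not stated; 10%, 20% and 30% are assumed.
- Fibrosis response rates among patients at stage 1 or above: not stated; 40% vs 15% and 50% vs 15% are used as illustrations.

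**Step 1: dilution.** With equal share *f* in both arms, each arm's rate is p(1 − f), so

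difference on all patients = (p1 − p0)(1 − f)

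For 40% vs 15%:
- f = 10%: 25 × 0.9 = 22.5 points
- f = 20%: 25 × 0.8 = 20.0 points
- f = 30%: 25 × 0.7 = 17.5 points

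The risk ratio is p1(1 − f) / [p0(1 − f)] = p1/p0. The factor cancels: 2.67 for 40% vs 15% and 3.33 for 50% vs 15%, at any *f*.

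**Step 2: power.** Exact Fisher test, two-sided 0.05. The restricted analysis has 26(1 − f) patients per arm, rounded to 23, 21 and 18.

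| f | 40% vs 15%: all 26 | 40% vs 15%: stage ≥1 | 50% vs 15%: all 26 | 50% vs 15%: stage ≥1 |
|---|---|---|---|---|
| 10% | 35% | 37% | 62% | 64% |
| 20% | 30% | 33% | 53% | 58% |
| 30% | 25% | 27% | 44% | 50% |

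Restriction never loses power here despite the smaller denominator. The gain is about 2 to 6 points.

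**Step 3: chance imbalance.** Suppose 10 of the 52 are stage 0 and allocation is random with respect to stage 0. A split at least as uneven as 3 vs 7 then has hypergeometric probability 0.29. With a common 30% response at stage 1 or above and no drug effect, a 3 vs 7 split gives 23 × 0.30/26 = 26.5% vs 19 × 0.30/26 = 21.9%, a gap of 4.6 points.

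For scale, at an average rate of 0.30 × 0.80 = 24%, the standard error of the difference is √(2 × 0.24 × 0.76/26) = 11.8 points. The gap is well under half of that.

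**Step 4: type I error.** With f = 20% and 30% response at stage 1 or above in both arms, Fisher rejects 2.3% of the time on all 26 per arm and 2.3% on 21 per arm at stage 1 or above. Test size is the same either way.

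**The case against.** The case for leaving item 1 alone has several parts.

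- **Importance.** Section 2 does not name fibrosis among its key secondary hypotheses, and Section 9.2 calls the categorical secondary analysis unpowered. A reader might infer from its first place in the list that outcome 1 is a main aim of the trial; the Protocol does not support that. This stands, and limits the weight of the point.
- **Effect measure.** Section 9.2 also plans relative risks, and the sensitivity analysis pools log risk ratios. These are not diluted when stage 0 is balanced. This stands: the dilution applies to the difference in proportions, and the loss of power to its test.
- **Imbalance.** A reader might infer that pooling stage 0 with stages 1-2 biases the comparison. It does not. Randomisation makes uneven splits symmetric, test size is preserved, and an ordinary confidence interval covers the gap. What remains is noise that the restricted definition would remove.
- **Small gain.** A few points of power on an unpowered outcome is little. That is true, but the change costs almost nothing.
- **Inference.** The Protocol nowhere says that stage 0 patients are non-responders; the missing-data rule concerns absent biopsies. The reading follows from the unrestricted definition, and a statistical analysis plan not shown could restrict it. However, the Protocol itself fixes the denominators of the next two outcomes, so item 1 should be equally explicit.
- **Already covered in part.** The two restricted outcomes exclude stage 0, and the Kleiner stage is analysed in its own right. Neither gives a one-stage improvement rate in all patients with fibrosis at baseline.
- **All randomised patients.** Keeping everyone avoids subsetting on one pathologist's baseline reading. That is defensible as a supportive analysis. Baseline stage is set before randomisation, so restricting on it keeps the comparison randomised.

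**Conclusion.** The point holds as a modest flaw in one definition. Followed literally, outcome 1 includes patients who cannot respond, unlike the two outcomes listed after it. The difference in proportions is multiplied by one minus the stage 0 share: 25 points becomes 22.5 to 17.5 at 10-30%. At 20% stage 0, Fisher power is 3 to 5 points lower than it need be.

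These sizes rest on an assumed stage 0 share and assumed response rates. If no stage 0 patient enters, the effect is nil. The documents do not support a claim that the treatment effect is diluted on every scale or that the fibrosis comparison is biased. The primary outcome, the sample size and the 8-of-21 rule are not affected.

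**What to change.** In Section 7, state that outcome 1 is assessed in randomised patients with baseline fibrosis stage 1 or above, with a missing end-of-treatment biopsy counted as non-response as Section 9.3 already provides. Report the result in all randomised patients as supportive.

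The cost is one line of text and a slightly smaller denominator: about 21 instead of 26 per arm if 20% are stage 0. No possible responder is lost, and no new data are needed.
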